4.5.5. Electrocardiograms

The 12-lead ECGs were performed at screening and at periodic time points throughout selpercatinib treatment. An ECG assessment was also done at the safety follow-up visit if treatment-emergent abnormalities were found at the end-of-treatment visit.

The following ECG parameters and clinical findings were collected:

- Heart rate (beats per minute)
- PR interval (milliseconds)
- R wave-to-R wave (RR) interval (milliseconds)
- QRS interval (milliseconds)
- QT interval (milliseconds)
- QTcF interval (milliseconds)

If QTcF is not reported, Frederica's correction to the reported QT interval will be derived (in milliseconds) for all patients and time points as follows:

$$QTcF (ms) = \frac{QT (ms)}{\sqrt[3]{RR (ms)/1000}}$$

If the R wave-to-R wave (RR) interval is not reported, it will be derived from the reported heart rate (HR) as follows for the derivation of RR:

$$RR (ms) = 1000 * \frac{60}{HR (bpm)}$$

All components for these calculations must be taken from the same assessment, which will be identified in the database by the date-time of the ECG recording.

The mean of the replicate ECG measurements will be used for the analysis whenever replicates are reported for a patient and time point (scheduled or unscheduled).

Each ECG parameter will be summarized in a descriptive manner by calculating the mean, standard deviation, median, and range of the following values that are derived for each patient:

- baseline value
- minimum postbaseline value and corresponding change
- maximum postbaseline value and
- last postbaseline value

Categorical analyses of the QTcF interval data across time points will be performed using shifts from baseline for the number and percentage of patients meeting or exceeding the following threshold values:

4.5.6. Extent of Exposure

Exposure to selpercatinib will be summarized based on the following:

- time on treatment
- dose intensities
- dosage modifications

4.5.6.1. Time on Treatment

TOT will be summarized descriptively. For patients who permanently discontinued selpercatinib as of the data cutoff date, TOT will be calculated as follows:

$$\text{TOT (months)} = (\text{Last Dose Date} - \text{First Dose Date} + 1) / 30.4375$$

The last dose date reported on the End of Treatment case report form will be used. For patients continuing to receive selpercatinib as of the data cutoff date, TOT will be calculated as follows:

$$\text{TOT (months)} = (\text{Data cutoff Date} - \text{First Dose Date} + 1) / 30.4375$$

4.5.6.2. Dose Intensities

Selpercatinib dose intensities will be summarized descriptively as ADI, PDI, and RDI.

- The ADI of selpercatinib (mg/day) will be calculated as the actual cumulative dose of LOXO-292 (mg) received divided by TOT (days).
- The PDI of selpercatinib (mg/day) will be as follows:
 - For once daily dosing schedule, the PDI (mg/day) = assigned dose level (mg)/day
 - For BID dosing schedule, the PDI (mg/day) = assigned dose level (mg) x 2/day
 - PDI will be calculated taking into account the starting dose and the escalated dose if applicable
- The RDI is the percentage of dose received relative to the planned dose through to treatment discontinuation and is defined as follows:

$$\text{RDI (\%)} = (\text{ADI} / \text{PDI}) * 100\%$$

4.5.6.3. Dose Modifications

The number and percentage of patients with dose reductions, dose withheld, and dose increases will be tabulated with the reason for each dose modification.

4.6. Other Analyses

4.6.1. Subgroup analyses

Supportive analyses will be performed to assess the safety and tolerability of selpercatinib across selected subgroups and special populations. These analyses will be conducted using the Safety Analysis Set. The incidence of treatment-emergent AEs and SAEs will be calculated for the subgroups and special populations defined by the following:

- age at enrollment (<65 years, ≥65 years)

- sex (male, female)
- race (White, other)

Depending upon the requests or requirements of individual regulatory authorities, age groupings other than those specified above may be utilized for supplemental analyses. The decision to combine selected categories and the manner in which they may be combined will be deferred until the analysis.

4.7. Changes to Protocol-Planned Analyses

Efficacy analyses will be performed by proposed indication instead of protocol-defined cohorts.

5. Supporting Documentation

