### **2.3 Primary Objective (Phase 2)**

- To assess, for each Phase 2 expansion cohort, the anti-tumor activity of selpercatinib by determining ORR using RECIST 1.1 or RANO, as appropriate to tumor type, as assessed by independent review committee (IRC).

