Selpercatinib will be administered in oral form at the dose determined during dose escalation (MTD or recommended dose for further study). Each cycle will consist of either 28 days or 84 days, depending on the patient's duration on treatment (see [Section 7](#)). Patients treated during Phase 1 at the dose chosen for further study and who also meet the criteria for one of the Phase 2 cohorts may be considered as part of the evaluable patients for that cohort.

The study drug schedule and treatment assessments for Phase 2 are described in [Section 6.2.3](#) and [Table 7-1](#), respectively.

A statistical justification for cohort size is discussed in [Section 8.3](#).

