## *Phase 2*

For Cohort 1 (patients with RET fusion-positive solid tumors who have progressed on or are intolerant to standard first-line therapy for their cancers), a true ORR of  $\geq 50\%$  is hypothesized when selpercatinib is administered to patients with such malignancies. A sample size of 55 patients is estimated to provide 85% power to achieve a lower boundary of a two-sided 95% exact binomial confidence interval (CI) about the estimated ORR that exceeds 30%. Ruling out a lower limit of 30% is considered clinically meaningful and consistent with the estimated response rates seen with approved targeted therapies in molecularly-defined patient populations who have failed prior therapies (e.g., osimertinib [Tagrisso®], crizotinib [Xalkori®], alectinib [Alecensa®], and others).

For Cohort 2 (patients with RET fusion-positive solid tumors without prior standard first-line therapy), a true ORR of  $\geq 55\%$  is hypothesized when selpercatinib is administered to such patients. A sample size of 59 patients is estimated to provide 85% power to achieve a lower boundary of a two-sided 95% exact binomial CI about the estimated ORR that exceeds 35%. For Cohort 3 (patients with RET-mutant MTC who have progressed on or are intolerant to vandetanib and/or cabozantinib), a true ORR of  $\geq 35\%$  is hypothesized when selpercatinib is administered to such patients. A sample size of 83 patients is estimated to provide 85% power to achieve a lower boundary of a two-sided 95% exact binomial CI about the estimated ORR that exceeds 20%. Ruling out a lower limit of 20% is considered clinically meaningful in patients who have failed prior MKI therapy (e.g., cabozantinib) and currently have limited treatment options for their advancing disease.

For Cohort 4 (patients with RET-mutant MTC who are MKI-naïve), a true ORR of  $\geq 50\%$  is hypothesized when selpercatinib is administered to such patients. A sample size of 55 patients is estimated to provide 85% power to achieve a lower boundary of a two-sided 95% exact binomial CI about the estimated ORR that exceeds 30%.

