### **8.5.3      *Efficacy Analyses***

The efficacy analyses will be conducted on the Safety Analysis Set of patients with at least 6 months of treatment from the first dose of selpercatinib. These analyses will be summarized per tumor indication, including patients from both the Phase 1 and Phase 2 portions. A Statistical Analysis Plan (SAP) will provide specific details on the efficacy analysis set.

ORR will be assessed using RECIST 1.1 ([Table 11-9](#)) or RANO ([Table 11-11](#), for patients with primary CNS tumors), as appropriate to tumor type. The estimate of the ORR will be calculated based on the maximum likelihood estimator (i.e., crude proportion of patients with best overall response of CR or PR that are confirmed based on RECIST 1.1 or RANO). The estimate of the ORR will be accompanied by 2-sided CIs with various coverage probabilities (e.g., 80%, 95%). The analysis of ORR will be conducted both by the responses determined by each Investigator and responses as determined by IRC.

Waterfall plots will be used to depict graphically the maximum decrease from baseline in the sum of longest diameters of target lesions.

DOR will be calculated for patients who achieve CR or PR. For such patients, DOR is defined as the number of months from the start date of CR or PR (whichever response status is observed first) and subsequently confirmed, to the first date that PD is objectively documented. If a patient dies, irrespective of cause, without documentation of PD beforehand, then the patient's date of death will be used to denote the response end date.

PFS will be derived for each patient as the number of months from the date of the first dose of study drug to the earlier of documented PD or death due to any cause. Patients who are alive and without documented PD as of a data analysis cutoff date will be right-censored according to the censoring methods described later in this section. Whenever appropriate, the same censoring methods will be used for DOR.

OS will be derived for each patient as the number of months from the date of the first dose of study drug to the date of death, irrespective of cause. Patients who are alive or lost to follow-up as of a data analysis cutoff date will be right-censored. The censoring date will be determined from the last date the patient was known to be alive or data analysis cutoff date, whichever occurs first.

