2.1. Safety Analysis Set

[Table JZJA.2.1](#) provides an overview of the safety analysis set.

Table JZJA.2.1. Description of Safety Analysis Sets

Safety Analysis Set	Analysis Set Description
Overall Safety Analysis Set	All patients who received at least 1 or more doses of selpercatinib regardless of diagnosis or line of therapy
RET fusion-positive NSCLC safety analysis set	All patients with RET fusion-positive NSCLC who received at least 1 dose of selpercatinib. This is a subset of the Overall Safety Population.
RET mutant MTC safety analysis set	All patients with RET mutant MTC who received at least 1 dose of selpercatinib. This is a subset of the Overall Safety Population.
RET fusion-positive thyroid safety analysis set	All patients with RET fusion-positive thyroid who received at least 1 dose of selpercatinib. This is a subset of the Overall Safety Population.
RET mutant non-MTC safety analysis set ^a	All patients with RET mutant non-MTC who received at least 1 dose of selpercatinib. This is a subset of the Overall Safety Population.
Prior RET inhibitor safety analysis set ^a	All patients who have received prior treatment with a selective RET inhibitor. This is a subset of the Overall Safety Population. This group includes patients with RET fusion-positive NSCLC, RET fusion-positive Thyroid and RET mutant MTC.

Abbreviations: MTC = medullary thyroid cancer; NSCLC = non-small cell lung cancer; *RET* = Rearranged during Transfection.

^a Selected safety analyses will be performed.

As of the data cutoff, enrollment is still ongoing for *RET* fusion-positive cancer other than NSCLC and thyroid cancer and the safety analysis and efficacy analysis on the population will be included in the respective CSR.

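### The Phase 2 primary objective and sizing are per cohort, but ORR is analysed only by tumor indication across all Phase 1 starting doses, so no planned table reports the cohort ORR the trial was sized on

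*SAP*

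**What the plan says.** **Per cohort.** Protocol 2.3 states the Phase 2 primary objective as "To assess, for each Phase 2 expansion cohort, the anti-tumor activity of selpercatinib by determining ORR using RECIST 1.1 or RANO", assessed by the independent review committee (IRC). Protocol 8.3 then sizes each of Cohorts 1-4. For Cohort 1, "A sample size of 55 patients is estimated to provide 85% power to achieve a lower boundary of a two-sided 95% exact binomial confidence interval" above 30%. The bounds for Cohorts 2, 3 and 4 are 35%, 20% and 30%. Protocol 3.6 lets some Phase 1 patients count as evaluable in a cohort, on conditions of dose and eligibility: "Patients treated during Phase 1 at the dose chosen for further study and who also meet the criteria for one" (that is, one cohort).

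**Per indication.** Protocol 8.5.3 summarises efficacy by tumor indication, "including patients from both the Phase 1 and Phase 2 portions"; the synopsis says the same. SAP 4.7 reads "Efficacy analyses will be performed by proposed indication instead of protocol-defined cohorts". SAP 2.2 admits anyone with at least one dose and six months of potential follow-up (or earlier progression or death). It groups patients by diagnosis and prior therapy, with separate sets for non-measurable disease and CNS metastases. It has no term for cohort, phase or starting dose.

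**Inference.** SAP 4.3.1 gives ORR with a two-sided 95% exact binomial interval and names no bound. The subgroup section, SAP 4.6.1, covers safety only.

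**Deferred tumors.** For fusion-positive cancers other than NSCLC and thyroid, SAP 2.1 says "the safety analysis and efficacy analysis on the population will be included in the respective CSR".

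**The concern.** The protocol asks one question and the analysis plan answers a nearby one. The unit of the primary objective, and of all four sample-size justifications, is the cohort. The unit of every planned efficacy table is an indication set with different membership rules. A reader of the final report could not look up the result for any protocol cohort or see it beside the bound for which that cohort was sized.

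The second gap is dose. Protocol 3.6 ties the counting of Phase 1 patients in a cohort to treatment at the dose chosen for further study. The indication sets carry no such condition, and Phase 1 starting doses ran from 20 mg QD to 240 mg BID (protocol Table 3-1). With no RP2D-only version of any efficacy table, the report could not show whether the pooled ORR matches the ORR in patients who started at 160 mg BID.

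**Working it through.** **1. Do the protocol's figures reproduce?** Inputs are from protocol 8.3. For each cohort, take the smallest responder count r whose Clopper-Pearson 95% lower limit exceeds the bound. Power is P(X ≥ r) with X ~ Binomial(n, assumed ORR).

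| Cohort | n | Bound | Assumed ORR | r | Lower limit at r | Power |
|---|---|---|---|---|---|---|
| 1 | 55 | 30% | 50% | 24 | 30.3% | 86.0% |
| 2 | 59 | 35% | 55% | 29 | 35.9% | 84.9% |
| 3 | 83 | 20% | 35% | 25 | 20.5% | 85.3% |
| 4 | 55 | 30% | 50% | 24 | 30.3% | 86.0% |

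The stated 85% holds in each case, so the four bounds are the criteria behind the sample sizes. They do not appear in the SAP.

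**2. Can a cohort be recovered from the SAP sets?**

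- *Cohorts 1 and 2* (fusion-positive solid tumors, treated and untreated) are split into NSCLC and thyroid sets by prior therapy. Their other tumor types go to another study report (SAP 2.1). Protocol Table 3-3 also bars FISH-only fusions from Cohorts 1 and 2 while allowing them in Phase 1 and Cohort 5; the SAP sets make no such distinction.
- *Cohort 3* is close to the MTC set previously treated with cabozantinib and/or vandetanib, but that set has no dose condition.
- *Cohort 4* is close to the MTC set without those two drugs. Cohort 4 also excludes other kinase inhibitors with anti-RET activity (protocol 3.6) and requires radiographic progression within 14 months (protocol 4.2). The SAP set allows other prior systemic therapy and has no progression requirement.

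The MTC sets therefore approximate Cohorts 3 and 4, and nothing in this report corresponds to Cohorts 1 and 2.

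**3. Does any other planned analysis fill the gap?** Futility monitoring (protocol 8.4) looks at response by cohort. It counts confirmed or unconfirmed responses against a 10% null, so it is neither the confirmed IRC ORR nor a check of the 20-35% bounds.

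**4. How large could the dose effect be?** If a share f of a set started at another dose,

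pooled ORR − RP2D ORR = f × (other-dose ORR − RP2D ORR).

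Neither term is available by set. The nearest figures are:

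- Protocol 3.6.1: 89 patients enrolled when the RP2D was selected, 24 of them at 160 mg BID, so 89 − 24 = 65 at other doses.
- Protocol 1.7: 825 patients treated as of 8 May 2022.
- 65/825 = 7.9%. Adding the three patients treated at 200 mg BID gives 68/825 = 8.2%.

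At about 8%, every 10 points of ORR difference between dose groups (an assumed scale) would move a pooled ORR by 0.08 × 10 = 0.8 points. If response does not depend on dose, the shift is zero. The share in a given set may be well above or below 8%.

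**The case against.** **The protocol itself plans indication-level analysis.** This is true, and it changes where the fault lies. Protocol 8.5.3 and the synopsis already pool phases by indication, and SAP 4.7 openly discloses the departure from cohorts. A reader might infer a late regrouping introduced by the SAP. The documents do not support that: protocol version 11.0, whose change log records updated language in 8.5.3, is dated 20 October 2022, before the SAP approval of 19 December 2022, and SAP versions 1 and 2 are not available. The conflict is protocol 2.3 and 8.3 against protocol 8.5.3 and SAP 2.2 and 4.7.

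**The same interval is still planned.** This is partly right. Protocol 8.3 describes sizing and states no separate test or decision rule. SAP 4.3.1 gives the same exact interval, so the MTC results can be compared with 20% and 30% by eye. The populations differ, however, and Cohorts 1 and 2 have no counterpart.

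**Protocol 3.6 does not forbid pooling.** Correct. Its wording is permissive and concerns cohort membership. It does not bar a pooled indication analysis, which protocol 8.5.3 expressly provides.

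**Dose pooling may matter little.** This may be so. A reader might take 65/89 (73%) as the off-dose share of the analysed patients. It is not a share of any efficacy set, because early Phase 1 did not require a RET alteration (protocol 3.4, 4.1). Intra-patient escalation was allowed, and some starting doses were above 160 mg BID, so even the direction of any bias is unknown. A serious loss of power is also not shown. An assumed 5-point fall from 50% to 45%, tested against 30%, leaves power of 91.9% at n = 125 and 99.8% at n = 250, the current caps for Cohort 4 and Cohort 1.

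**A cohort table would be incomplete and mixed.** This stands as a reason to make it supportive. Cohorts 1 and 2 combine lung, thyroid, colorectal, pancreatic and other tumors, and some of those are deferred.

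**Conclusion.** The inconsistency is real and worth correcting. The plan as written has no analysis that reports its stated Phase 2 primary objective by cohort, none that sets an ORR against the 8.3 bounds, and none that isolates patients who started at the RP2D. This rests on the text alone and needs no assumption about response by dose.

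Its effect on the reported ORR is undetermined. The overall off-dose share of about 8% assumes that the 65 patients at RP2D selection stand for all non-RP2D starters and that the 825 treated are the right denominator; neither is shown for any analysis set. The documents do not support a claim that the pooled ORR is biased downward, or that the indication sets are the wrong main presentation.

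**What to change.** Keep the indication sets as the main presentation and add to SAP 4.3.1:

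- **(a) A supportive cohort table.** Report IRC ORR with exact 95% CI for protocol Cohorts 1-4 in patients who started at the RP2D (Phase 2 patients plus Phase 1 patients who qualify under protocol 3.6), beside the 30%, 35%, 20% and 30% bounds. Mark Cohorts 1 and 2 as excluding the tumors deferred to another study report until those data are available.
- **(b) A sensitivity analysis.** Repeat ORR for each indication set in patients who started at the RP2D, and state how many patients in the set started at other doses.

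Then reconcile protocol 2.3 and 8.3 with protocol 8.5.3 and SAP 4.7, so that the objective, the sizing and the analysis name the same unit.

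The cost is a few tables from existing data and a short SAP paragraph, with no further patients. The drawback is that the Cohort 1 and 2 results would be incomplete in this report and must be labelled so.

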5.1. Appendix 1: Demographic and Baseline Characteristics

Baseline characteristics of patients included in the safety analysis set will be summarized in a tabular manner for the following factors:

- demography
- cancer and other relevant medical history
- prior cancer treatments
- *RET* alteration

5.1.1. Demography

The following variables will be summarized across patients to describe the demographics and other characteristics at enrollment:

- Age at enrollment - summarized as a continuous variable in years relative to the date informed consent is signed. Age will also be summarized categorically based on the following age groups:
 - <18 years
 - 18 to <45 years
 - 45 to <65 years
 - 65 to <75 years
 - ≥75 years
- sex (male, female)
- race (White, Black, Asian, other)
- ethnicity (Hispanic or Latino, not Hispanic or Latino, declines to state)
- height (cm)
- weight (kg)
- body mass index
- performance status – will be presented using the ECOG scale; data collected using the Lansky scale will be mapped to ECOG using published methods

5.1.2. Cancer History

The following variables will be summarized across patients to describe the types of cancers:

- primary cancer diagnosis (standardized term)
- stage of disease at initial diagnosis (I–IV)
- time since initial diagnosis (years)
- metastatic disease at enrollment (yes, no)
- time since initial diagnosis of metastatic disease (years)

5.1.3. Prior Cancer Treatment

The following variables will be summarized across patients to characterize the extent of prior cancer treatments:

- prior radiotherapy (yes, no)
- prior cancer-related surgery (yes, no)
- prior systemic treatments (yes, no)
- number of prior systemic regimens or treatment courses (0, 1, 2, ≥ 3)
- number of prior systemic regimens or treatment courses (as a continuous variable)
- BOR and discontinuation of the last therapy prior to enrollment

Prior systemic cancer therapies will be assigned standardized terms by the medical monitor.

5.1.4. RET Alteration Status

The *Ret* fusion partner will be summarized.

5.1.5. Noncancer Medical History

Noncancer medical history will be displayed in patient listing format.

5.2. Appendix 2: Protocol Deviation

Protocol deviations will be identified and reported by the process described in the current version of the study Protocol Deviation Plan. The number and percentage of patients with reported protocol deviations will be tabulated by category. Protocol deviations will be listed by patient.

6. References

- [FDA] United States Food and Drug Administration. Guidance for industry: drug-induced liver injury: premarketing clinical evaluation. July 2009. Accessed December 15, 2022. <https://www.fda.gov/media/116737/download>

Signature Page for VV-CLIN-075801 v1.0

Approval	
PPD
 
19-Dec-2022 20:26:13 GMT+0000

----------	---

Signature Page for VV-CLIN-075801 v1.0
